4.7.2. Sensitivity Analyses

To determine robustness of results, the sensitivity analyses will be performed for the primary efficacy endpoint, Schirmer test at visit 7 (week 12) and all other post-baseline visits (Visit 3, Visit 4, Visit 5, Visit 6, and Visit 8), on the mITT and PP populations by using:

- 1. last observation carried forward (LOCF)
- 2. observed data only
- 3. FCS MI.

As sensitivity analyses, LOCF, observed data, and FCI MI will be analyzed in a manner similar to the primary efficacy variable (details in section 4.7.1). For the unadjusted treatment group comparisons analyses using LOCF and observed data, in addition to t-test, Wilcoxon rank sum test will be run on the treatment group combinations.

4.7.3. Secondary Analyses

1. To analyze the efficacy endpoint of percent of eyes with ≥10 mm Increase in Schirmer Test from Baseline at Visit 7 (Week 12) and other Post-Baseline Visits, the logistic regression or Fisher's exact test will be used as described below:

The two groups of Schirmer test (≥10 mm vs <10 mm) will be compared between treatment groups as CSI Formulation 1 to HV Formulation 2B, CSI Formulation 2A to HV Formulation 2B, CSI Formulation 1 to HV Formulation 3, CSI Formulation 2A to HV Formulation 3, will be reported. This model will also be used to compare overall OTX-CSI (combined Formulation 1 and Formulation 2A) to each HV Formulation (2B and 3) using the logistic regression.

The above analyses will be performed on the change from baseline in Schirmer test (\geq 10 mm vs <10 mm) derived based on the imputed Schirmer data using FCS MI (details in section 4.2.9.1) at visit 7 on the mITT and PP populations using the logistic regression and Odds Ratio (OR), 95% confidence interval for OR, and P-value for OR will be reported. In addition, sensitivity analyses will be done using LOCF and observed data and the two groups of Schirmer test (\geq 10 mm vs <10 mm) will be compared between treatment groups using the Fisher's exact test on this endpoint. These analyses will also be performed on all post-baseline visits.

2. To analyze the efficacy endpoints of Eye Dryness Severity and Eye Dryness Frequency, statistical modeling similar to the primary efficacy endpoint analysis (4.7.1) will be performed for each post-baseline visit (Visit 3, Visit 4, Visit 5, Visit 6, Visit 7, and Visit 8)

Sponsor:	Ocular Therapeutix, Inc.		
Protocol:	CLN-Protocol-0054		
Document Version No.:	V1.0 Document Date: 01-OCT-2021		

using the MCMC MI imputed data on the mITT and PP populations. In addition, sensitivity analyses done for the primary efficacy endpoint will also be performed on this endpoint.

3. To analyze the efficacy endpoints of total Corneal Fluorescein Staining (tCFS) and its sub-region, statistical modeling similar to the primary efficacy endpoint analysis (4.7.1) will be performed for each post-baseline visit (Visit 3, Visit 4, Visit 5, Visit 6, Visit 7, and Visit 8) using the MCMC MI imputed data on the mITT and PP populations. In addition, sensitivity analyses done for the primary efficacy endpoint will also be performed on this endpoint.

The rest of secondary efficacy endpoint analysis of below parameters will be done similar to analysis of Schirmer test using observed data, for each post-baseline visit (Visit 3, Visit 4, Visit 5, Visit 6, Visit 7, Visit 8, and 30-Day Follow-Up) on mITT and PP populations using observed data:

1. Conjunctival Lissamine Green Staining using NEI scale

2. Ocular Surface Disease Index questionnaire (OSDI©) (total score, each of the three domains and the individual questions)

3. SPEED measures (overall score and individual questions) and its CFB

4.7.4. **Exploratory Analyses**

The exploratory analyses will be done on mITT populations for both study and non-study eye.

The Tear Film Break Up Time at Week 12 and its CFB will be summarized using descriptive statistics (the number of subjects, mean, SD, median, minimum and maximum) by treatment group and overall. Tear Film Break Up Time at Week 12 will be analyzed similar to analysis of Schirmer test using observed data.

Ease of insertion as assessed by the Investigator at Visit 2 or Visit 2B, presence of insert and ease of visualization as assessed by the Investigator at all post-baseline visits will be summarized using discrete statistics (number and percentage) and will be tested between treatment groups (CSI Formulation 1 to HV Formulation 2B, CSI Formulation 2A to HV Formulation 2B, CSI Formulation 1 to HV Formulation 3, CSI Formulation 2A to HV Formulation 3, will be reported. This model will also be used to compare overall OTX-CSI (combined Formulation 1 and Formulation 2A) to each HV Formulation (2B and 3). To analyze ease of insertion as assessed by the Investigator and ease of visualization as assessed by the Investigator, Pearson Chi-squared test will be used. To analyze presence of insert, Fisher's exact Test will be used.

Sponsor:	Ocular Therapeutix, Inc.		
Protocol:	CLN-Protocol-0054		
Document Version No.:	V1.0 Document Date: 01-OCT-2021		

4.8. **Pharmacokinetic Evaluations**

PK analysis will be described separately.

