2. STUDY DESIGN

2.1. Synopsis of Study Design

This is a randomized, multi-center, double-masked, vehicle-controlled, phase 1/2 clinical study designed to evaluate the safety, tolerability, and efficacy of OTX-CSI (cyclosporine ophthalmic insert) for intracanalicular use for the treatment of subjects with DED. Approximately 145 subjects (290 eyes) will be enrolled in this study at approximately 15 sites in the US.

Subjects will be enrolled in two cohorts. Cohort 1 will be an open-label group consisting of approximately 5 subjects. Cohort 2 will be a randomized, double-masked group consisting of approximately 140 subjects treated with 2 different hydrogel formulations of OTX-CSI and 2 different formulations of hydrogel vehicle inserts (HV). Both eyes will be treated with the same treatment/formulation.

Cohort Number	Number of Subjects	Treatment	Formulation
1 Open-label	5	OTX-CSI	2A
2 Randomized, double-masked	40	OTX-CSI	1
	40	OTX-CSI	2A
	40	HV	2B
	20	HV	3

Cohort 1

Subjects in Cohort 1 will undergo Screening 14 days prior to Insertion/Day 1 (Visit 2) to determine eligibility and eligibility will be re-confirmed at Visit 2 (Insertion/Day 1). The treatment follow-up visits will occur at Week 2 (Visit 3), Week 4 (Visit 4), Week 6 (Visit 5), Week 9 (Visit 6), Week 12 (Visit 7), and Week 16 (Visit 8). All subjects in Cohort 1 will be followed until Week 16 (Visit 8) whether or not an insert is visualized.

Cohort 2

Subjects in Cohort 2 will undergo Screening 14 days prior to Insertion/Day 1 (Visit 2) to determine eligibility. At Visit 2 (Insertion/Day 1) eligibility will be confirmed and subjects who are eligible will be randomly assigned to one of four treatment groups (OTX-CSI Formulation 1, OTX-CSI Formulation 2A, HV Formulation 2B or HV Formulation 3) in a 2:2:2:1 ratio. Should only a unilateral insertion be possible, Visit 2B will occur within 3 days to attempt the insertion again. The treatment follow-up visits will occur at Week 2 (Visit 3), Week 4 (Visit 4), Week 6 (Visit 5),

Sponsor:	Ocular Therapeutix, Inc.			
Protocol:	CLN-Protocol-0054			
Document Version No.:	V1.0	Document Date:	01-OCT-2021	

Week 9 (Visit 6), Week 12 (Visit 7), and Week 16 (Visit 8). All subjects in Cohort 2 will be followed until Week 16 (Visit 8) whether or not an insert is visualized.

[figure not shown]

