2.3. Randomization Methodology and Masking

Cohort 1 will be open-label and treatment assignment will be known to the sponsor, investigator and subjects. All 5 enrolled subjects in Cohort 1 will receive OTX-CSI Formulation 2A.

Cohort 2 will be randomized to treatment assignment and double-masked.

A randomization schedule will be computer-generated by a qualified biostatistician independent of the study conduct or project team and uploaded into the EDC system. The EDC/IRT system will be used for randomization and unmasking. At Visit 2 (Insertion/Day 1) eligibility will be confirmed and subjects who are eligible will be randomly assigned to one of four treatment groups (OTX-CSI Formulation 1, OTX-CSI Formulation 2A, HV Formulation 2B or HV Formulation 3) in a 2:2:2:1 ratio.

The HV and OTX-CSI inserts administered to subjects at randomization in the double-masked treatment phase will be comparable in appearance. Study subjects and investigators and their staff will be masked to the identity of treatment until the final database is locked. The Sponsor's personnel involved with the conduct and monitoring of the study will remain masked until completion of the study and database lock.

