4.2. General Statistical Methods and Data Handling

4.2.1. **General Methods**

All output will be incorporated into Microsoft Excel or Word files, sorted, and labeled according to the International Council on Harmonisation (ICH) recommendations, and formatted to the appropriate page size(s).

Tabulations will be produced for appropriate demographic, baseline, efficacy, pharmacokinetic and safety parameters. For categorical variables, summary tabulations of the number of missing, and number and percentage of each category of the parameter will be presented by treatment groups and visits (as applicable). For continuous variables, the n, mean, standard deviation, median, minimum, and maximum values will be presented.

The baseline visit will be defined as the last non-missing measure prior to initiation of investigational treatment. Differences between treatment groups will be calculated as OTX-CSI minus HV, and change from baseline will be calculated as follow-up visit minus baseline visit values.

All statistical testing will be done at the two-sided alpha level of 0.05.

Sponsor:	Ocular Therape	Ocular Therapeutix, Inc.			
Protocol:	CLN-Protocol-0054				
Document Version No.:	V1.0	V1.0 Document Date: 01-OCT-2021			

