5. CHANGES TO PLANNED ANALYSES

The language in the SAP will supersede the language in the protocol should there be a discrepancy.

The primary analysis will be repeated for all visits using observed data (without imputation) for both mITT and PP populations. These results will be provided in sensitivity analyses section.

The difference between two OTX-CSI hydrogel formulations as well as the difference between two HV formulations will not be studied. HV formulations will not be combined.

Wilcoxon rank sum test will be used only to analyze LOCF and observed data.

For Eye Dryness Severity and Eye Dryness Frequency, as well total Corneal Fluorescein Staining (tCFS) and its sub-region the main analysis will be based on MCMC MI and sensitivity analyses will be done using LOCF, observed data, and FCS.

For the first secondary efficacy endpoint analysis, for the main analysis, the two groups of change from baseline in Schirmer test (\geq 10 mm vs <10 mm) at visit 7 will be compared between treatment groups using the logistic regression and for the sensitivity analyses, the groups will be compared using LOCF and observed data by Fisher's exact test; Clopper-Pearson method will be used to calculate 95% confidence interval of the proportion of subject with change from baseline in Schirmer Test \geq 10 mm; to calculate 95% confidence interval of the proportion difference, the Chan and Zhang (1999) method will be used.

These analyses will also be performed on all post-baseline visits.

Sponsor:	Ocular Therapeutix, Inc.		
Protocol:	CLN-Protocol-0054		
Document Version No.:	V1.0 Document Date: 01-OCT		01-OCT-2021

6. **REFERENCES**

American Academy of Ophthalmology Cornea/External Disease Panel. Preferred Practice Pattern[®] Guidelines. Dry Eye Syndrome. San Francisco, CA: American Academy of Ophthalmology; 2018. Available at www.aao.org/ppp. Accessed September 23, 2019.

- Disease in the United States Among Adults Aged 18 Years and Older. Am J Ophthalmol. Oct;182:90-98.
- Perry HD. Dry eye disease: Pathophysiology, classification, and diagnosis. Am J Manag Care. 2008;14:S79-S87.
- Schultz C. Safety and efficacy of cyclosporine in the treatment of chronic dry eye. Ophthalmol Eye Dis. 2014;6:37-42.

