7.3.6. SAS codes to generate and pool proportions using MI data

```
proc surveyfreq data= pr1fcsy;
            by avisitn imput;
            tables TRPG1*CRIT8 / row ;
            ods output CrossTabs=mi_perc_out;
```

run;

```
proc mianalyze data=mi_perc_out;
    by TRPG1 CRIT8;
    modeleffects RowPercent;
    stderr RowStdErr;
    ods output ParameterEstimates=pooled_percent;
run; quit;
```

7.3.7. SAS codes to generate and pool the Odds Ratio (OR) using MI data

```
ods output ParameterEstimates =OR_out;

proc surveylogistic data= pr1fcsy;

by avisitn imput;

class TRPG1 / param = ref;

model CRIT8 (desc) =TRPG1;

where TRPG1N in (1 3);

run;

proc mianalyze data=OR_out;
```

```
modeleffects Estimate ;
stderr StdErr;
ods output ParameterEstimates=pooled_OR;
```

run; quit;

Sponsor:	Ocular Therapeutix, Inc.			
Protocol:	CLN-Protocol-0054			
Document Version No.:	V1.0	Document Date:	01-OCT-2021	

7.3.8. SAS codes to output 95% CI for proportions using Clopper-Pearson method and 95% CI for the proportion difference using Chan and Zhang (1999) method using observed and LOCF data

ods output RiskDiffCol1=RiskDiffCol1 FishersExact=FishersExact;
proc freq data=adoe;

table TRPG1N* CRIT8 / fisher;

exact riskdiff(method=score);

run;

7.3.9. SAS codes to designate study eye randomly in a case both eyes have the same total corneal fluorescein staining score

- 1- Create a SAS dataset RND1 with 1000 observations,
- 2- Create a variable named FOCID. The first 500 observation with value of "OD" (Right Eye) the last
- 500 observation with value of "OS" (Left Eye)
- 3- Generate a random number using RANUNI (Uniform distribution)
- 4- Sort this dataset by random variable ****;

data rnd1;

```
do i=1 to 500;
FOCID="OD";
rand=ranuni(54603);
output;
end;
do i=501 to 1000;
FOCID="OS";
rand=ranuni(54603);
output;
end;
run;
proc sort data=rnd1(drop=i); by rand; run;
data rnd1; set rnd1; VSORT= n ; run;
proc sort data=rnd1; by VSORT; run;
****
5- Sort the subject by using 2 variables
```

```
a- date of randomization for randomized subjects / date of informed consent for open label subjects
```

- b- random number
- c- subject number

Sponsor:	Ocular Therapeutix, Inc.			
Protocol:	CLN-Protocol-0054			
Document Version No.:	V1.0	Document Date:	01-OCT-2021	

6- Then merge this dataset with RND1 and then selected FOCID will be their study eye.****; proc sort data=idsd.suppdm out=dm1(keep=USUBJID QVAL);

where QNAM="RANDNUMB";

by USUBJID;

run;

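### The main responder analysis has no rule for an arm with no responders; in the n=20 vehicle arm that is plausible and would make the pooled odds ratio uninterpretable

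*SAP*

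**What the plan says.** SAP 4.7.3 compares responders (Schirmer gain from baseline of at least 10 mm) between arms at Week 12 and the other post-baseline visits, in mITT and PP, on FCS-imputed data, "using the logistic regression and Odds Ratio (OR), 95% confidence interval for OR, and P-value for OR will be reported". SAP 5 confirms that this is the main analysis. SAP 4.2.2 extends all endpoints to both eyes, analysed separately.

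SAP 7.3.7 calls "proc surveylogistic data= pr1fcsy" with "model CRIT8 (desc) =TRPG1", restricted to two arms at a time and run in each imputed set before pooling. It has no penalised or exact option.

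Cohort 2 has "approximately 140 subjects treated with 2 different hydrogel formulations of OTX-CSI" and two vehicle formulations. Its last-listed arm is "HV Formulation 3) in a 2:2:2:1 ratio", so F3 has 20 subjects (SAP 2.1 table). Because "HV formulations will not be combined" (SAP 5), F3 stands alone as comparator in three contrasts: Formulation 1, Formulation 2A, and the two combined.

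Fisher's exact test is assigned to the LOCF and observed-data sensitivity analyses (SAP 4.7.3, 5). The Clopper-Pearson and Chan-Zhang intervals are coded for the same data only (SAP 7.3.8). Neither document says what to do if an arm has no responders.

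**The concern.** With no responders in one of two arms, the logistic likelihood has no maximum at a finite log odds ratio. The printed value depends on when the iterations stop. The pooled result takes one log OR and standard error from each of 25 imputed sets, so a single such set contaminates it.

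A low F3 rate is plausible from the documents. The study eye enters with Schirmer above 0 and at most 10 mm (Protocol 7.1), so a response at least doubles the baseline. F3 carries no drug and is designed to last about 1 week, while the endpoint is at Week 12.

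At stake are the OR, interval and p-value of the first-listed secondary endpoint in the F3 contrasts, tested under the rule "All statistical testing will be done at the two-sided alpha level of 0.05". A rescue method chosen after unmasking would be post hoc.

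**Working it through.** **Inputs from the documents:** about 140 subjects at 2:2:2:1 (SAP 2.1, 2.3); 25 imputations (SAP 4.2.9.1); vehicles not combined (SAP 5). **Assumed:** responder rates, the example tables and the stopping iteration. SAP 4.1 reports no sample-size calculation.

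**1. Arm sizes.** 140 × 2/7 = 40 and 140 × 1/7 = 20, which reproduces the plan's 40/40/40/20.

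**2. Chance of an empty responder cell,** (1 − p)^n:

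| Assumed rate p | 0 of 20 (F3) | 0 of 40 (F2B) |
|---|---|---|
| 2% | 0.67 | 0.45 |
| 5% | 0.36 | 0.13 |
| 10% | 0.12 | 0.015 |
| 15% | 0.04 | 0.002 |

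0 of 20 is more likely than not only if p < 1 − 0.5^(1/20) = 3.4%. It falls below 10% once p > 1 − 0.1^(1/20) = 10.9%. If imputed values follow the true rate, the table approximates the chance for one imputed set. The chance that at least one of 25 sets is empty cannot be smaller.

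**3. The estimate with a zero cell.** Newton-Raphson for 6/40 v 0/20:

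| Iterations | log OR | Model-based SE |
|---|---|---|
| 8 | 7.47 | 22.3 |
| 15 | 14.47 | 738 |
| 25 | 24.47 | 109,489 |

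It does not converge.

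**4. Pooling, model-based SE.** Let 24 sets show 6/40 v 1/20: log OR = ln[(6/34)/(1/19)] = 1.21, SE = √(1/6 + 1/34 + 1/1 + 1/19) = 1.12. Let one set show 6/40 v 0/20, stopped at 8 iterations.
- Mean log OR = (24 × 1.21 + 7.47)/25 = 1.46.
- Within variance = (24 × 1.25 + 22.3²)/25 ≈ 21.1.
- Between variance = (7.47 − 1.21)²/25 ≈ 1.57.
- Total = 21.1 + 1.04 × 1.57 ≈ 22.7, so SE ≈ 4.76.

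The pooled OR moves from 3.4 (0.38 to 30) to 4.3 (0.0004 to 49,000).

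**5. If the procedure uses a robust variance** (a software assumption; the SAP does not say). For 4/40 v 0/20 the sandwich variance of the log OR tends to (1/4 + 1/36 + 1/20) × 60/59 = 0.333, so SE = 0.577. Against a log OR of 7.0 (8 iterations) or 14.0 (15 iterations), p < 0.0001. Fisher's exact test on the same table gives p = 0.29.

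Pooled over 25 sets (6/40 v 0 or 1 of 20, stopped at 15 iterations), p depends on how many sets have the empty cell:

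| Empty-cell sets of 25 | Pooled p |
|---|---|
| 0 | 0.28 |
| 1 | 0.55 |
| 13 | 0.24 |
| 20 | 0.034 |
| 25 | below 0.0001 |

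False significance therefore needs most sets to be empty, as when F3 has few or no missing values.

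**6. Candidate repairs.** For two arms, Firth's estimate adds one half to each cell. For 6/40 v 0/20, OR = (6.5/34.5)/(0.5/20.5) = 7.7 (0.39 to 155).

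| Table | Firth-Wald p | Fisher p |
|---|---|---|
| 2/40 v 0/20 | 0.54 | 0.55 |
| 4/40 v 0/20 | 0.30 | 0.29 |
| 6/40 v 0/20 | 0.18 | 0.17 |
| 8/40 v 0/20 | 0.12 | 0.043 |

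Risk difference for 6/40 v 0/20:
- Plain Wald: 0.15 ± 1.96 × √(0.15 × 0.85/40 + 0) = 0.04 to 0.26. The empty arm adds no variance, and the interval excludes zero although Fisher p = 0.17.
- Agresti-Caffo (one success and one failure added per arm): 7/42 − 1/22 = 0.121; variance = 0.167 × 0.833/42 + 0.045 × 0.955/22 = 0.0053; interval −0.02 to 0.26.

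**The case against.** A reader might infer that zero responders in F3 is likely. The documents do not support that: they give no responder rate, and the chance is only 4% at a 15% rate. Study eyes are selected for low Schirmer, so some upward regression to the mean is expected in every arm. Protocol 4.2 also treats punctal occlusion as effective, although F3 is designed to last only about a week. Plausible is the word the material supports.

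A reader might also infer that the endpoint would be left without a valid analysis. It would not. Fisher's test is planned for this endpoint on LOCF and observed data, with exact intervals for each proportion and for the difference, and SAP 7.3.6 already pools responder proportions across imputations. The opening of 4.7.3 names logistic regression or Fisher's test, which could be read as a choice. The text that follows assigns Fisher only to the sensitivity analyses, so it is not a fallback for the imputed analysis.

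The importance is bounded. This is a secondary endpoint in a Phase 1/2 trial without multiplicity control. The primary ANCOVA is unaffected, and the F2B contrasts are much less exposed.

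Finally, one cannot say that the standard error will diverge. That holds for a model-based variance; a robust one fails the other way. Both make the result unusable. The objection to a simple Firth swap also stands in part: its Wald p-value is conservative with a zero cell, so it should not be the only result read.

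**Conclusion.** The gap is real and worth closing before unmasking. The main imputed responder analysis relies on an estimator with no finite value at a zero cell, uses a 20-subject comparator in three of six contrasts, and names no fallback. At assumed F3 rates of 5% to 10%, the chance of 0 of 20 is 36% to 12%; it exceeds one half only below 3.4%. If an imputed set has a zero cell, the pooled OR, interval and p-value for that contrast cannot be interpreted.

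The size of the risk rests on assumed rates. Steps 3 and 4 rest on arithmetic and an assumed stopping iteration. The falsely small standard error rests on an assumption about the software's variance and, after pooling, on most imputed sets having the empty cell. The sensitivity analyses limit the damage but do not repair the main result.

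**What to change.** 1. In SAP 7.3.7, replace PROC SURVEYLOGISTIC with PROC LOGISTIC and the FIRTH option in each imputed set, then pool the treatment log OR. The documents describe no survey design that calls for the survey procedure.
2. Add a risk difference pooled across imputations, with a variance that stays above zero at 0/n (for example Agresti-Caffo), not the plain Wald variance.
3. State in SAP 4.7.3 that when an arm has no observed responders, the already planned Fisher test and Chan-Zhang interval on observed data are read alongside the pooled OR.

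The cost is one changed procedure call, one added estimate and one sentence. The price is some shrinkage of the OR and a conservative Wald p-value when a cell is zero: 0.12 against Fisher's 0.043 for 8/40 v 0/20. That is why item 3 is needed.

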11.6 Missing Data

The primary analyses of efficacy data will use Markov Chain Monte Carlo (MCMC) multiple imputation methodology to impute missing data. Sensitivity analyses, to determine robustness of results, will be performed using last observation carried forward (LOCF) and observed data only.

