11.7 Efficacy Analyses

The primary efficacy endpoint analysis of Schirmer Test will use a linear model with fixed effects of baseline Schirmer Test value and treatment will be used to compare Schirmer Test change from baseline and absolute values with least square means comparing OTX-CSI treatment groups to HV treatment groups at each visit. In addition to looking at the individual formulations, the two formulations of OTX-CSI and HV will be combined and a linear model, two-sample t-test and Wilcoxon rank sum test will be performed at each visit.

Secondary efficacy endpoint analyses of Total Corneal Fluorescein Staining (tCFS) using NEI scale, CFS sub-regions using NEI scale, Conjunctival Lissamine Green Staining using NEI scale, Eye Dryness Score (VAS) and Ocular Surface Disease Index questionnaire (total score, each of the three domains and the individual questions) will be analyzed similar to the Schirmer Test. Speed measures (overall score and individual questions) will also be analyzed similarly, however only change from baseline will be presented. Percent of subjects with ≥ 10 mm increase in Schirmer at Week 12 will be analyzed using a chi-squared test.

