11.8 Exploratory Analyses

Tear Film Break Up Time at Week 12 will be analyzed similar to the Schirmer Test, however only observed data will be used. Presence of insert, ease of insertion as assessed by the Investigator and ease of visualization as assessed by the Investigator at all post-baseline visits will be summarized using discrete statistics and will be tested between treatment groups (all treatment groups separately and combined) using the Pearson chi-squared statistic.

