11.9 Reporting Deviations

Should there be changes in any analyses described in the protocol, the statistical analysis plan will document them. Should there be changes in any analyses described in the statistical analysis plan, the final clinical study report will describe them.

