4.2.9.1. Imputation Method for Efficacy Endpoints

To impute missing, Markov Chain Monte Carlo (MCMC) multiple imputation (MI), Fully Conditional Specification multiple imputation (FCS MI) and last observation carried forward (LOCF) methods will be used.

For MI, we will have below phases:

1. Imputation Phase: in this phase, the missing data will be imputed using SAS PROC MI and a complete data set will be created. This process of imputation will be repeated 25 times. Therefore, 25 compete datasets will be created. In this phase, treatment group, baseline value, and post-baseline visits from visit 3 to visit 8, respectively, will be included in multiple imputation model.

2. Analysis Phase: each of the 25 complete data sets will be analyzed independently using desired statistical method (e.g. ANCOVA for primary efficacy analysis).

3. Pooling Phase: in this phase the estimates obtained from each analyzed complete dataset from phase 2, will be combined using PROC MIANALYZE.

The analysis of efficacy variables Schirmer Test, Eye Dryness Severity Score and Eye Dryness Frequency Score on mITT and PP populations will be performed by imputing missing data using MCMC MI methodology with repeated 25 times of imputation under the assumption of missingness at random. Last observation carried forward (LOCF) method and Fully Conditional Specification multiple imputation (FCS MI) with 200 burn-in iterations and 25 times of imputation under the assumption of missingness at random will be used for sensitivity analyses (Section 4.7.2). LOCF method will be used for sensitivity analyses.

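### SAP analyses lissamine staining, OSDI and SPEED on observed data only, where the protocol makes multiple imputation the main method, and SAP Section 5 does not list the change

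*SAP*

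**What the plan says.** **Protocol.** Section 11.6 states: "The primary analyses of efficacy data will use Markov Chain Monte Carlo (MCMC) multiple imputation methodology to impute missing data". Its sensitivity analyses "will be performed using last observation carried forward (LOCF) and observed data only". Section 11.7 then lists lissamine staining and OSDI among the secondary endpoints that "will be analyzed similar to the Schirmer Test. Speed measures (overall score and individual questions) will also be analyzed similarly". The one difference it gives for SPEED is that only change from baseline is presented. Where the protocol wants an observed-data analysis it says so, and it does this once, in 11.8: "Tear Film Break Up Time at Week 12 will be analyzed similar to the Schirmer Test, however only observed data will be used". Section 11.9 adds: "Should there be changes in any analyses described in the protocol, the statistical analysis plan will document them".

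**SAP.** Section 4.2.9.1 assigns MCMC imputation by name: "The analysis of efficacy variables Schirmer Test, Eye Dryness Severity Score and Eye Dryness Frequency Score on mITT and PP populations will be performed" that way. Section 4.7.3 also gives imputation to corneal staining and its sub-regions. For lissamine staining, OSDI and SPEED, 4.7.3 says the analysis "will be done similar to analysis of Schirmer test using observed data, for each post-baseline visit", on the mITT and PP populations.

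Section 5 (Changes to Planned Analyses) has imputation entries for VAS dryness, corneal staining and the Schirmer responder endpoint. Its one statement about data without imputation concerns the repeat of the primary analysis. Lissamine staining, OSDI and SPEED do not appear there.

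**The concern.** Three groups of secondary endpoints move from an imputed main analysis to observed data alone, and they also lose the LOCF analysis that the protocol planned. They are left with one missing-data approach and nothing to test it against, while VAS dryness and corneal staining get MCMC imputation plus LOCF, observed-data and FCS analyses. No reason is given for the split.

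The observed-data model at each visit conditions on treatment and baseline only. It is unbiased if, given those two, missingness is unrelated to the score at that visit. The SAP's imputation model also uses the other post-baseline visits, so it needs missing at random given those visits too, which is a weaker requirement. If subjects whose recent scores are poor are more likely to leave, the two approaches can give different answers. OSDI and SPEED carry most of the patient-reported evidence besides VAS.

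**Working it through.** **Step 1: the texts side by side.** The plan gives no figure on this point to reproduce. The comparison is:

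| Endpoint | Protocol main method | SAP main method | SAP sensitivity analyses | Named in SAP Section 5 |
|---|---|---|---|---|
| VAS dryness | MCMC MI (11.6, 11.7) | MCMC MI | LOCF, observed, FCS MI | Yes |
| Corneal staining and sub-regions | MCMC MI | MCMC MI | LOCF, observed, FCS MI | Yes |
| Lissamine staining | MCMC MI | Observed | None | No |
| OSDI | MCMC MI | Observed | None | No |
| SPEED | MCMC MI | Observed | None | No |
| TBUT (exploratory) | Observed (11.8) | Observed | None | Not needed |

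The SAP table list (7.1) agrees. Tables 14.2.3.12.x (lissamine), 14.2.3.14.x (OSDI) and 14.2.3.16.x (SPEED) have no MCMC, FCS or LOCF versions. Schirmer, VAS and corneal staining have all of them.

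**Step 2: what each model uses.** By SAP 4.2.5 and 4.7.1 the analysis model contains treatment and the baseline value. By SAP 4.2.9.1 the imputation model contains treatment, baseline and Visits 3 to 8. The difference is the post-baseline history.

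**Step 3: how much that could matter.** The documents give no dropout rate, SD or between-visit correlation, so every input here is an assumption:

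- true effect 0.5 SD;
- Week 9 to Week 12 correlation 0.7;
- correlation of baseline with later visits 0.3 to 0.7;
- dropout before Week 12 depending on the Week 9 score, log-odds 0.5 to 1.0 per SD, same mechanism in both arms, giving 9 to 24% dropout;
- large samples (400,000 per arm), so that sampling error is negligible.

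Results for the Week 12 contrast:

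- Observed data, adjusted for baseline as the SAP plans: about 0.46 to 0.50 SD, or about 1 to 7% too small. The loss shrinks as baseline correlation rises: 0.468 to 0.499 at 0.4, and 0.489 to 0.500 at 0.7, where the mildest settings lose almost nothing.
- Imputation from the earlier visit: about 0.50 SD throughout.
- Observed data without the baseline covariate: 0.459 to 0.494 SD, so (0.500 − 0.459)/0.500 = 8% at worst. This is not the planned model.

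**Step 4: against the precision of the trial.** In SD units, with n per arm and baseline correlation r, the standard error of the adjusted contrast is about √(2/n) × √(1 − r²).

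- n = 40, r = 0.3: 0.224 × 0.954 = 0.213.
- n = 40, r = 0.7: 0.224 × 0.714 = 0.160.
- After 24% dropout in each arm, n = 40 × 0.76 = 30.4 and r = 0.3: 0.256 × 0.954 = 0.245.

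The largest bias is 0.07 × 0.5 = 0.035 SD, and it arises at low r. Against 0.213 it is 0.16 of a standard error; against 0.245 it is 0.14. For combined OTX-CSI against Formulation 2B (80 against 40, r = 0.3) the standard error is √(1/80 + 1/40) × 0.954 = 0.194 × 0.954 = 0.185, and the ratio is 0.19.

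**The case against.** The strongest reply is that nothing is hidden. SAP 4.7.3 states the observed-data method openly, and Section 5 opens by saying that the SAP prevails over the protocol. Protocol 11.9 asks the SAP to document changes without saying where. This stands in part: the governing method is clear and was fixed in advance, so a reader who infers that the analysis is undefined would be wrong. But the precedence clause neither identifies this change nor gives a reason for it, in a section that itemises imputation for the other secondary endpoints.

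It can also be argued that Protocol 11.6 means the primary endpoint only. The wording allows that, but the instruction in 11.7 to follow Schirmer, and the separate observed-data exception for TBUT, make it the less natural reading.

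Three stronger readings are tempting and are not supported:

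- *OSDI and SPEED cannot be compared with VAS.* They can. VAS on observed data is planned in Tables 14.2.3.6.1 and 14.2.3.6.2, and corneal staining on observed data in Tables 14.2.3.10.x.
- *Subjects will leave for lack of benefit, more of them on vehicle.* The documents give no dropout rates or reasons. Treatment is a single insertion session, follow-up runs to Week 16 whether or not an insert is seen, artificial tears are allowed if needed, and early leavers are asked to complete the Visit 8 assessments.
- *The bias is large.* If only vehicle dropout depended on the last score (vehicle 13 to 24%, active 10%), the contrast would be 0.456 to 0.472 SD at baseline correlation 0.7 and 0.387 to 0.433 at 0.4, that is 6 to 23% too small. The differing persistence of the inserts makes arm-specific dropout conceivable, but nothing in the documents establishes it.

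**Conclusion.** The point holds as a departure from the protocol's missing-data method that Section 5 neither lists nor explains, and for which a better method is already written into the SAP. Its likely size is small: about 1 to 7% of a 0.5 SD effect, at most about a fifth of a standard error. That rests on the assumed effect, correlations and dropout, on dropout depending on the previous score, and on the same mechanism in both arms. If little data are missing, or missingness does not depend on earlier post-baseline scores, the bias disappears.

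These are secondary endpoints in a Phase 1/2 study with no formal sample size and no multiplicity adjustment. The primary Schirmer analysis is unaffected. The change is worth making because it is cheap.

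**What to change.** In SAP 4.7.3 and 4.2.9.1, make the existing MCMC imputation the main analysis for the lissamine total, the OSDI total and three domains, and the SPEED total. Keep observed data and LOCF as sensitivity analyses, as Protocol 11.6 intends. The code in SAP 7.3.2 can be re-used with its limits changed from the Schirmer range to 0–18 for lissamine (Protocol Appendix 7), 0–100 for OSDI and 0–28 for SPEED (SAP 2.6.1.2).

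Keep observed data for the individual OSDI and SPEED questions and for the 30-day visit. Protocol 11.7 treats the individual questions like the totals, so list that remaining departure in Section 5 with a reason. While editing 4.2.9.1, add corneal staining to its list of imputed variables; 4.7.3 and Section 5 already include it.

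The cost is some extra tables from existing code, and a short entry in Section 5.
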